### 10.1.6 Death

All subject deaths during this study will be collected and presented in a listing. The information that is presented includes date of death, days on study, cause of death, and relationship of death to study drug.

## 16.1.9 Documentation of Statistical Methods

Receptos, Inc.  
Protocol RPC01-201

Statistical Analysis Plan – Part A, V1.2  
Date Issued: May 20, 2014

### 10.1.7 Adverse Events of Special Interest

Target AEs of special interest will be closely monitored in the study. These AEs include infections, malignancies, cardiac (bradycardia and heart conduction abnormalities), pulmonary function (decline in FEV1, FVC, and DLCO measurements), ophthalmic (macular edema), hepatic (LFTs elevation), and dermatological (cutaneous malignancy) abnormalities. These AEs will be summarized in tables.

## 10.2 Clinical Laboratory Evaluations

Laboratory assessments will be performed by a central laboratory. Unless otherwise specified, all summaries will be based on the SI units provided by the central lab.

Summary tables including actual values and change from baseline values will be presented for clinical laboratory tests with numeric values by treatment group. Laboratory data will be summarized using shift tables where appropriate. Each subject's hematology and blood chemistry values will be flagged as "low", "normal", or "high" relative to the normal ranges of the central laboratory or as "unknown" if no result is available. Each subject's urinalysis values will be flagged as "positive", "negative", or if no value is available, "unknown".

### 10.2.1 Hematology

The following laboratory tests will be included for hematology summary tables: red blood cell (RBC) count, total and differential WBC count (basophils, eosinophils, lymphocytes, monocytes, and neutrophils), platelet count, hemoglobin, hematocrit, mean corpuscular volume (MCV), mean corpuscular hemoglobin (MCH), mean corpuscular hemoglobin concentration (MCHC), and RBC morphology. A listing will present abnormal hematology values for all subjects.

Subjects with abnormalities in hematology assessments, defined as absolute lymphocyte count (ALC) <200 cells/uL, absolute neutrophil count (ANC) < 500 cells/uL as well as ANC <1000 cells/uL and total WBC >20,000 cells/uL will be summarized for each treatment group.

In addition, the change and percent change from baseline in CBC with Differential will be summarized for each treatment group.

### 10.2.2 Blood Chemistry

The following laboratory tests will be included for blood chemistry summary tables: sodium, potassium, chloride, calcium, magnesium, phosphate, blood urea nitrogen, random glucose, albumin, alkaline phosphatase, creatinine, SGPT/ALT, SGOT/AST, gamma glutamyltransferase (GGT), amylase, total bilirubin, conjugated bilirubin, hemoglobin A1c. A Listing will present abnormal chemistry values for all subjects.

## 16.1.9 Documentation of Statistical Methods

Receptos, Inc.  
Protocol RPC01-201

Statistical Analysis Plan – Part A, V1.2  
Date Issued: May 20, 2014

The incidence of subjects with abnormalities in Liver Function Tests (SGPT/ALT, SGOT/AST, and GGT) will be summarized overall and at each visit for each treatment group for the following categories:

- $\geq 1 \times$  upper limit of normal (ULN)
- $\geq 2 \times$  ULN
- $\geq 3 \times$  ULN
- $\geq 4 \times$  ULN
- $\geq 5 \times$  ULN

### 10.2.3 Urinalysis

Summary statistics for each visit and change from baseline will be presented for specific gravity and pH. Shift table will be presented for leukocytes, bilirubin, blood, glucose, ketones, protein, and urobilinogen.

## 10.3 Vital Sign Measurements

Vital signs including standing and supine systolic blood pressure (SBP), standing and supine diastolic blood pressure (DBP), body temperature, and heart rate (HR) will be recorded on the eCRF once per visit at Screening, Week 4, Week 8, Week 12, Week 16, Week 20, and Week 24. In addition, pre-dose and hourly cardiac monitoring (blood pressures and heart rates) for hours 1-6 will be recorded for all patients at the baseline visit and for the first 75 patients on Days 5 and 8.

Summary tables including actual values and change from baseline (defined as pre-dose on Day 1) values will be presented for vital signs including SBP (supine and standing), DBP (supine and standing), temperature, and HR by treatment group for the Safety population. On Day 1, hourly changes from pre-dose in blood pressures and heart rates will be shown for all patients. For all other visits starting at Week 4, only a single timepoint will be collected and shown.

For patients participating in cardiac monitoring on Days 5 and 8, a summary table will be provided that summarizes the hourly change from pre-dose assessment through hour 6 at each of the baseline, Day 5, and Day 8 visits by treatment group for heart rate and blood pressure.

Box plots will be provided to display the distribution of vital signs. In addition, line plots will be created to display the change from baseline over the entire study period and change from pre-dose in vital signs for the baseline, Day 5, and Day 8 visits.

The number and percentage of subjects with SBP  $> 180$  mmHG or  $< 90$  mmHG and HR  $< 40$  beats per minute will be summarized by visit for each treatment group. The number and percentage of subjects with clinically relevant abnormalities will be presented by treatment group. The criteria for clinically relevant abnormalities are shown in the following table. Vital signs will be presented by subject in listings.

## 16.1.9 Documentation of Statistical Methods

Receptos, Inc.  
Protocol RPC01-201Statistical Analysis Plan – Part A, V1.2  
Date Issued: May 20, 2014**Table 10.3.1 Criteria to Determine Clinically Relevant Abnormalities in Vital Signs**

Vital Sign	Criteria for Abnormalities
Temperature	>38°C and an increase from pre-dosing of at least 1°C
Heart Rate	>120 beats per minute post-baseline, or an increase from pre-dosing of more than 20 beats per minute, or <45 beats per minute post-baseline, or a decrease from pre-dosing of more than 20 beats per minute
Systolic Blood Pressure	>180 mmHg post-baseline, or an increase from pre-dosing of more than 40 mmHg, or <90 mmHg post-baseline, or a decrease from pre-dosing of more than 30 mmHg
Diastolic Blood Pressure	>105 mmHg post-baseline, or an increase from pre-dosing of more than 30 mmHg, or <50 mmHg post-baseline, or a decrease from pre-dosing of more than 30 mmHg

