10.2.1.1. Guidelines for Monitoring Patients Taking Their First Dose of RCP1063

On Day 1 of treatment, careful cardiac monitoring of the patients is required. The treating physician is responsible for monitoring the patient following the first intake of the study drug, as well as managing bradycardia symptoms should they occur. He or she must review the baseline predose ECG, vital signs during the 6-hour monitoring period, post-dose ECG, and assess discharge status at 6 hours after dosing. Baseline predose ECG should be provided by the site and be available for comparison to the postdose ECG in order to determine if criteria requiring extended monitoring are met. In addition, continuous Holter monitoring will be performed beginning 15 minutes predose and for 24 hours after dose administration. Further details on ECG and Holter monitoring procedures are provided in the Holter Manual.

Heart rate, blood pressure, and other vital signs will be measured before the first dose of study drug, then every hour for at least 6 hours thereafter (by the treating physician or an assisting nurse). Blood pressure and heart rate will be measured in the supine position and then the standing position at each time point. When obtaining the predose heart rate before the first dose, the patient should be allowed to rest in the supine position for 10 to 15 minutes before taking the heart rate. The supine heart rate and blood pressure measurements should be repeated 2 additional times to produce 3 readings for both heart rate and blood pressure (before the first dose of study drug only). The lowest predose value of supine heart rate and blood pressure (based on systolic blood pressure) will be recorded in the case report form and should be used for comparison to the postdose values. Orthostatic blood pressure will then be measured once with the patient in the standing position (after standing for 2 minutes) before the first dose of study drug.

Patients should receive the first dose of study drug in a fasted condition before 12:00 pm (noon) in the clinic. The first dose of RPC1063 should be administered in a setting in which resources to appropriately manage symptomatic bradycardia are available. A member of the Investigator team

should be available to monitor the patient for the 6 hours monitoring period and will need to report any abnormalities to the treating neurologist. Atropine needs to be readily available to the site personnel.

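### SAP Table 10.3.1 mixes heart-rate rises and falls in one abnormality, so its by-arm percentage can dilute, and under one pre-dose rule nearly mask, an excess of clinically relevant falls

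*SAP*

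**What the plan says.** The heart-rate row of SAP Table 10.3.1 joins four conditions by 'or'. Three of them are ">120 beats per minute post-baseline, or an increase from pre-dosing of more than 20 beats per minute, or <45 beats per minute post-baseline". The fourth is "or a decrease from pre-dosing of more than 20 beats per minute". Two conditions point up and two point down.

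SAP 10.3 then states: "The number and percentage of subjects with clinically relevant abnormalities will be presented by treatment group". It mentions neither direction nor visit, whereas the sentence just before it asks for heart rate below 40 bpm by visit.

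Readings are taken "once per visit at Screening, Week 4, Week 8, Week 12, Week 16, Week 20, and Week 24", and also hourly, "for hours 1-6 will be recorded for all patients at the baseline visit and for the first 75 patients on Days 5 and 8".

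The change limits are measured from pre-dosing. Protocol 10.2.1.1 asks for three supine pre-dose readings and says: "The lowest predose value of supine heart rate and blood pressure (based on systolic blood pressure) will be recorded in the case report form". On position it says: "Blood pressure and heart rate will be measured in the supine position and then the standing position at each time point". SAP 10.3 names both positions for blood pressure but gives none for heart rate.

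Bradycardia is an adverse event of special interest. SAP 10.1.7 says: "These AEs include infections, malignancies, cardiac (bradycardia and heart conduction abnormalities").

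**The concern.** The known drug effect has one direction. Protocol 7.2.4 reports a Day 1 titration change of -7.6 bpm on RPC1063 against -2.8 bpm on placebo. A criterion met by either a rise or a fall gains patients at one end and loses them at the other, so its total is a poor measure of either.

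This row is where the SAP counts patients with a clinically relevant heart-rate change. The 45 bpm limit also matters elsewhere: under Protocol 10.2.1.1 a rate below it at hour 6 calls for extended monitoring. In the SAP summaries that limit appears only inside the two-way criterion. A reader comparing arms on this percentage could see little difference while noticeably more RPC1063 patients had a qualifying fall.

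**Working it through.** The documents give no expected rate for this criterion, so there is no planned figure to reproduce. The check applies Table 10.3.1 to simulated patients.

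**From the documents**
- Readings per patient: 6 hourly on Day 1 + 6 visits (Weeks 4 to 24) = 12. The first 75 patients have more.
- Net Day 1 effect (Protocol 7.2.4): -7.6 - (-2.8) = -4.8 bpm.
- Patients per arm: 70.

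**Assumed, because the documents do not give them**
- Mean heart rate 74 bpm, between-patient SD 9, floor 58.
- Within-patient SD of 6, 8, 10 or 12 bpm, its variance split equally between visit and reading.
- Day 1 placebo drift of 0 to -2 bpm.
- Drug shift of -2 bpm (hour 1), -3.5 (hour 2) and -5 (hours 3 to 6), then -3 or 0 at later visits. Protocol 12.4 says only that the effect appears to attenuate.

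**Model.** Reading = patient mean + visit deviation + reading deviation + shift, rounded to whole bpm. Low = any reading below 45 or more than 20 below pre-dose. High = any reading above 120 or more than 20 above pre-dose. Combined = low or high.

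**Reference = lowest of three pre-dose heart rates, later shift -3 bpm** (placebo vs drug, %, gap in points)

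| Within-patient SD | Combined | Gap | Low | Gap | High | Gap |
|---|---|---|---|---|---|---|
| 8 | 34.0 vs 32.2 | -1.8 | 8.4 vs 18.2 | +9.8 | 27.7 vs 16.9 | -10.8 |
| 10 | 60.5 vs 58.2 | -2.3 | 19.1 vs 32.4 | +13.3 | 48.3 vs 35.0 | -13.3 |
| 12 | 79.4 vs 77.9 | -1.5 | 31.2 vs 45.6 | +14.4 | 63.9 vs 51.6 | -12.3 |

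The gain in falls is roughly matched by the loss of rises. With 70 per arm, +10 to +14 points is 0.10 × 70 = 7 to 0.14 × 70 ≈ 10 more patients with a fall, which the combined row would not show. If the drug acts on Day 1 only, at SD 10 the figures are 61% vs 61% combined and 19% vs 26% low.

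**Reference = a single pre-dose reading, later shift -3 bpm.** At SD 8 the combined figure is 33% vs 42% (+9) and the low figure 19% vs 35% (+16). Over SD 8 to 12 the gaps are about +4 to +10 combined and +14 to +17 low. Repeat runs of this model differ by up to about 3 points, so these are approximate ranges.

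**Placebo rate.** With the lowest-of-three reference, the combined criterion is met by about 9% of placebo patients at SD 6 and 79% at SD 12.

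**Second model.** Mean 72 bpm, placebo drift -2.8 on Day 1, drug shift -4.8 on Day 1 and then 0 or -4.8. Its SD is that of a change from baseline, 8 to 14 bpm. Dividing by √2 gives 5.7 to 9.9 on the scale above.

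| Reference | Combined gap | Low gap |
|---|---|---|
| Lowest of three | 0 to +5 | +4 to +21 |
| Single reading | +8 to +17 | +8 to +24 |

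With a sustained -8 bpm shift the combined gap is visible under either reference: +7 to +15 (lowest of three) and +19 to +35 (single).

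**Is the count below 40 bpm a substitute?** In the second model at a -4.8 bpm shift it is met by about 0.2% to 6% of placebo and 1% to 14% of drug patients, so it misses most qualifying falls.

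**The case against.** **Pooling is inferred.** SAP 10.3 does not say outright that the four limits collapse into one percentage over all readings. Table shells are not in the documents and might separate them. That stands as a caution. Still, the table gives one row joined by 'or', and the text asks for subjects with abnormalities by arm. A single any-limit, any-time count is the natural reading.

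**The pre-dose rule decides the size.** A reader might infer that the criterion hides bradycardia. The documents do not support that. Protocol 10.2.1.1 selects the lowest pre-dose value on systolic pressure, and Protocol 11.2.1 repeats this. The recorded heart rate may therefore come from the lowest-systolic reading and behave like an ordinary single reading. The excess is then diluted but visible. Near-masking needs the lowest of three heart rates, which the wording also allows.

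**Most untreated patients meet it.** That too might be inferred, but it rests on a within-patient SD that appears nowhere in the documents.

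**Other displays show direction.** SAP 10.3 plans hourly Day 1 changes for all patients, heart rate below 40 by visit, box and line plots, and listings. SAP 10.1.7 tabulates the special-interest events, bradycardia included, and SAP 2 sends Holter heart rate to a separate plan. This stands, and it limits the point to one percentage. None of the summaries described counts patients below 45 bpm or with a fall above 20 bpm.

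**No testing.** SAP 10 rules out hypothesis tests on safety results, so power is not at issue. The concern is how the table reads.

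**Conclusion.** The point holds in a limited form. As written, the heart-rate percentage mixes directions and visits and can understate an excess of clinically relevant falls. With within-patient SDs of 8 to 12 bpm and a -3 bpm later effect, both assumed, the combined gap is about -2 points against +10 to +14 for falls with a lowest-of-three reference, and about +4 to +10 against +14 to +17 with a single reading. Which case applies cannot be settled, because the heart-rate reference is ambiguous and the SAP does not state the position. A larger sustained effect would show in the combined figure as well.

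The defect is one of reporting. It does not show that bradycardia would go unseen in Part A. The systolic and diastolic rows have the same two-way form, but no size was calculated for them.

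**What to change.** In SAP 10.3 and Table 10.3.1:
- Tabulate heart rate in two rows by arm: low (<45 bpm or a fall of more than 20 bpm) and high (>120 bpm or a rise of more than 20 bpm).
- Show Day 1 hours 1 to 6 apart from Week 4 onward, and say whether the Day 5 and Day 8 readings of the first 75 patients are counted.
- State which pre-dose heart rate is the reference and whether supine or standing readings enter the criterion.
- Split the systolic and diastolic rows by direction in the same way, for consistency, using the limits already listed.

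The combined percentage may stay as an extra row. The change uses the same data and alters no limit or clinical rule. Its cost is SAP wording and slightly longer safety tables.

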**10.4 Electrocardiogram**

Summary tables including actual values and change from baseline values will be presented for ECG results. The overall interpretation of the ECG results (Normal; Abnormal; not Clinically Significant; and Abnormal, Clinically Significant) will be summarized for each treatment group.

**10.5 Pulmonary Function Testing**

The following laboratory tests will be included for pulmonary function testing (PFT) summary tables: forced expiratory volume in 1 second (FEV1), forced vital capacity (FVC), and diffusing capacity of the lung for carbon monoxide (DLCO). For FEV1 and FVC, summary tables for actual value, change, percent change, percent predicted, change in percent predicted, and percent change in percent predicted will be produced. For DLCO summary tables for actual value, change, and percent change will be produced. DLCO is collected at the local lab for each site, so results may be collected in domestic or SI units. DLCO results in domestic units (mL/min/mmHg) will be converted to SI units (mmol/min/kPa) prior to analysis using the following conversion factor:

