Target AEs of interest in study RPCS 001 were closely monitored and included bradycardia and other heart conduction abnormalities, pulmonary toxicity, hepatotoxicity, macular edema, and suicidal ideation. No AEs were reported for LFT elevation, macular edema, or suicidal ideation. Two subjects who received 2 mg RPC1063 for 7 days had Grade 1 pulmonary-related adverse events of obstructive airways disorder. For the two subjects, forced vital capacity (FVC) and forced expiratory volume at 1 second (FEV₁) declined to >20% below their baseline values on Day 7 (last dosing day) and Day 14 (last post-dose follow-up visit). Subjects were followed and values returned to baseline off therapy.

Four subjects had Grade 2 cardiac-related AEs of bradycardia and/or conduction abnormality. One subject experienced a Grade 2 second degree AV block and associated nausea after receiving a single dose of 1.5 mg RPC1063 that led to study discontinuation. At a dose of 3 mg RPC1063, 2 subjects reported AEs of Grade 2 sinus arrest, and 1 subject reported an AE of sinus bradycardia. These events resolved within 24 hours with no medical intervention.

All subjects, including those administered placebo, showed an initial reduction in HR following dosing on Day 1. Subjects who received RPC1063 had a greater decrease in HR compared to placebo subjects, and there was evidence of a dose-dependent decrease in absolute heart rate. Lower doses of RPC1063 led to less change in absolute heart rate over time, with the greatest change from baseline during the first 12 hours following treatment of -5.2 bpm and -13.2 bpm for doses of 0.3 mg and 1 mg, respectively. In general, most of the decrease in HR was observed within the first 6 hours after study drug was administered.

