The technician should demonstrate the appropriate spirometry technique to the patient and follow the standard procedure. The quality of the tests must be accounted for including the technicians' comments (especially when, despite proper coaching of the patient, full collaboration cannot be achieved). A central trial statistician will calculate the FEV₁/FVC ratio.

A minimum of 3 acceptable maneuvers will be performed at each visit. The acceptability criteria are a satisfactory start of test and a satisfactory end of test. In addition, the technician should observe that the patient understood the instructions and performed the maneuver with a maximum inspiration, a good start, a smooth continuous exhalation, and maximal effort. The largest FVC and the largest FEV₁ will be recorded, after examining the data from all of the acceptable curves, even if the 2 values do not come from the same curve. Please refer to the American Thoracic Society/European Respiratory Society guidelines for standardization of spirometry and single breath determination of carbon monoxide uptake in the lung ([MacIntyre, 2005](#); [Miller, 2005a](#); [Miller, 2005b](#)).

If for any reason a patient is permanently discontinued from study medication the patient will have the pulmonary function tests performed at his last visit or within 30 days of the study drug discontinuation.

Two acceptable DLCO tests should be performed at each scheduled timepoint. A DLCO test is acceptable if it fulfills all the following criteria:

- Use of proper quality-controlled equipment
- Inspired volume of greater than 85% of largest vital capacity in less than 4 seconds

- A stable calculated breath hold for 10 (\pm 2) seconds. There should be no evidence of leaks or Valsalva or Mueller maneuvers
- Expiration in less than 4 seconds (and sample collection time less than 3 seconds), with appropriate clearance of dead space and proper sampling/analysis of alveolar gas.
- All values must be corrected for hemoglobin concentration in the study, using the central laboratory haemoglobin value for the respective visit.

Ophthalmological Examination

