 - In case of clinical symptoms or hypotension, administration of atropine 1 mg, repeated administration in 3-5 minutes.
 - If heart rate and/or blood pressure remains unresponsive, consider administration of dopamine drip 5-20 μ g/kg/min or epinephrine drip 2-10 μ g/min.
 - Performance of transcutaneous pacing may also be considered
 - In the setting of decreased blood pressure, isoproterenol should be avoided or used with caution.
- Any condition that might affect the outcome of pulmonary function testing (FEV₁ and FVC) including infection, respiratory symptoms, occupational exposures (including asbestos) and cigarette smoking, needs to be collected before every PFT testing and transcribed to the pulmonary function tests eCRF page. If patients have decline in PFT values (FEV₁ and/or FVC) below 50% of the predicted values, treatment should be discontinued. If a patient discontinues due to respiratory AE, the Investigator should ensure that the patient has adequate evaluations as clinically indicated by a pulmonologist (consider pulmonary function tests, chest X-ray or high resolution computed tomography, based on findings of the other exams) at the time of the AE. For patients with pulmonary nodules, lung biopsy should be considered (Cryptococcus pneumonia and pulmonary TB have been reported with fingolimod). Further evaluations will be conducted until such time as resolution is confirmed or no

CONFIDENTIAL

The information contained herein may not be used, disclosed, or published without the written consent of Receptos.

further improvement is expected by the investigator (based on a follow-up period of not less than 3 months).

- If patients have elevations in the LFTs (SGPT/ALT or/and SGOT/AST) greater than 3 times the ULN, a retest must be performed within 14 days. Upon confirmation of the abnormality, retests should be performed weekly until the elevated LFT decreases to below 3 times the ULN. If the LFT increase is confirmed to be above 5 times the ULN the study medication must be permanently discontinued.

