## 16.1.9 Documentation of Statistical Methods

Receptos, Inc.  
Protocol RPC01-201

Statistical Analysis Plan – Part A, V1.2  
Date Issued: May 20, 2014

Provided that the primary comparisons are statistically significant, the sequential testing procedure will continue to be used for the secondary endpoints. The prespecified order includes both the order of the secondary endpoints and dose groups. Specifically, for each of the secondary endpoints, a sequential testing procedure will be used to control the overall Type I error rate due to multiple comparisons with the first comparison (RPC1063 1 mg versus placebo) and the second comparison (RPC1063 0.5 mg versus placebo). Secondary endpoints have been rank prioritized in the order shown in [Section 8.2](#) of the protocol.

Unless specified otherwise, all statistical analyses will be performed using a two-sided hypothesis test at the overall 5% level of significance. Accordingly, p-values will be rounded to three decimal places. If a p-value is less than 0.001, it will be reported as “<0.001”. If a p-value is greater than 0.999, it will be reported as “>0.999”.

Continuous data will be presented using descriptive statistics: n, mean, standard deviation, median, minimum and maximum. Categorical data will be summarized by the number and percent. Confidence intervals (CIs) will be 95% and two-sided, unless otherwise stated. Data will be displayed in all listings sorted by treatment group and subject number. When count data are presented, the percent will be suppressed when the count is zero in order to draw attention to the non-zero counts. A row denoted “Missing” will be included in count tabulations where necessary to account for dropouts and missing values. The denominator for all percents will be the number of subjects in that treatment within the population of interest, unless otherwise stated. Non-zero percentages will be rounded to one decimal place, except 100% will be displayed without any decimal places. Additional rounding rules are as follows:

- If the original value has 0 decimal places: mean, median, and CIs will have one decimal place and SD will have 2 decimal places
- If the original value has 1 decimal place: mean, median, and CIs will have 2 decimal places and SD will have 3 decimal places
- If the original value has 2 or more decimal places: mean, median, CIs, and SD will all have 3 decimal places

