## 16.1.9 Documentation of Statistical Methods

Receptos, Inc.  
Protocol RPC01-201

Statistical Analysis Plan – Part A, V1.2  
Date Issued: May 20, 2014

$$\text{DLCO in SI units} = (\text{DLCO in domestic units}) / 2.986$$

Line plots of FEV1, FVC, and DLCO results over time will be presented. All PFT results will be listed.

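### SAP 10.5 shows the worst spirometry value per arm but not how many patients had a marked decline, and it omits the FEV1/FVC ratio that the protocol says will be calculated

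*SAP*

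**What the plan says.** - **Pulmonary tables.** SAP 10.5 says that for FEV1 and FVC "summary tables for actual value, change, percent change, percent predicted, change in percent predicted, and percent change in percent predicted will be produced". DLCO gets actual value, change and percent change. Line plots follow, and "All PFT results will be listed".
- **Statistics in those tables.** SAP section 5 sets the default: "Continuous data will be presented using descriptive statistics: n, mean, standard deviation, median, minimum and maximum".
- **Adverse events.** SAP 10.1.7 names "pulmonary function (decline in FEV1, FVC, and DLCO measurements") among the events of special interest and adds "These AEs will be summarized in tables". SAP 10.1.5 tabulates adverse events for which study drug was permanently stopped.
- **Counts elsewhere.** SAP 10.2.1 counts patients beyond lymphocyte, neutrophil and white-cell limits, SAP 10.2.2 those at 1 to 5 times the upper limit of normal for liver tests, and SAP 10.3 those beyond blood pressure and heart rate limits. SAP 10.5 has no such count.
- **Ratio.** Protocol 11.2.1 says "A central trial statistician will calculate the" FEV1/FVC ratio. SAP 10.5 does not mention it.
- **Phase 1 signal.** Protocol 7.2.4 reports that two subjects given 2 mg for 7 days "had Grade 1 pulmonary-related adverse events of obstructive airways disorder", with FEV1 and FVC both more than 20% below baseline and later recovery off treatment.
- **Protocol limit.** Protocol 9.4.4.1 and 12.4 set a limit for FEV1 or FVC; in the words of 12.4, "below 50% of the predicted values, treatment should be discontinued".

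**The concern.** The pulmonary risk described in the protocol is one of individual patients with large falls, not of a small shift in everyone. A safety reader will first ask how many patients per arm had such a fall, out of how many tested. No planned pulmonary table answers that, whether for a fall of the size seen in Phase 1 or for the protocol's own 50%-of-predicted limit.

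Adverse event tables fill the gap only in part. Protocol 12.5 and 12.7 make an abnormal result or finding an adverse event according to its symptoms, its need for treatment or its clinical significance in the investigator's view. A symptom-free fall that stays above 50% of predicted can therefore be measured, entered in the database and still be missing from every count. An objective tabulation does not depend on that judgement.

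**Working it through.** **Inputs.** Arm size 70 (protocol 13.2, SAP 5.1). Phase 1 falls of more than 20% in two subjects (protocol 7.2.4). Assumed, because the documents give neither: a fall of 25% (range 20% to 30%) in two patients, and an SD of percent change of 5 to 12 points.

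**1. Arm size.** Noether's formula: N = (1.960 + 0.842)² / (12 × 0.25 × 0.15²) = 116.3 in total, or 58.1 per group, rounded up to 59. Allowing for 15% dropout, 59/0.85 = 69.4, rounded up to 70. The plan's figure is reproduced. It serves here only as a denominator.

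**2. The mean.** Two falls of 25% shift the arm mean by 2 × 25/70 = 0.71 points (0.57 for falls of 20%, 0.86 for 30%). The standard error of a difference between two arms is SD × √(2/70):

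| SD | SE of difference | 0.71/SE |
|---|---|---|
| 5 | 0.85 | 0.85 |
| 8 | 1.35 | 0.53 |
| 10 | 1.69 | 0.42 |
| 12 | 2.03 | 0.35 |

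No test is planned on safety data (SAP section 10). The standard error is used only to show that the shift is within ordinary noise.

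**3. The minimum.** With those two patients the percent-change table would print -25% or lower, so the worst case is visible. It gives one value per arm and visit, however many patients fell. With no drug effect and normally distributed changes, the chance that an arm of 70 has a minimum of -20% or lower is 1 - [1 - Φ(-20/SD)]^70:

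| SD | Probability |
|---|---|
| 5 | 0.2% |
| 8 | 35% |
| 10 | 80% |
| 12 | 97% |

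Only at the low end of the assumed spread does the minimum alone separate a drug arm from placebo.

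**4. A count.** The same two patients would appear as 2/70 = 2.9%, beside the matching figure for placebo.

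**5. The ratio.** From an assumed starting ratio of 0.80:
- FEV1 and FVC both down 22%: 0.80 × 0.78/0.78 = 0.80.
- FEV1 down 25%, FVC down 21%: 0.80 × 0.75/0.79 = 0.76.
- FEV1 down 30%, FVC down 21%: 0.80 × 0.70/0.79 = 0.71.

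When both volumes fall together the ratio hardly moves. The reason to report it is the commitment in protocol 11.2.1, not that it would surely have shown the Phase 1 pattern.

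**The case against.** The strongest reply is that the information is already there. The minimum shows the worst fall and every result is listed. The Phase 1 cases were themselves recorded as adverse events, at Grade 1, and the same event in Part A would enter the general and special-interest tables. A value below 50% of predicted is listed in protocol 9.4.4.1 among the special-interest events that are reasons to stop study drug, so many such patients would also appear in the SAP 10.1.5 table. This stands. A reader might infer that lung function is summarised by means alone, or that the harm would be invisible; the documents support neither. What remains open is the frequency of falls short of the 50% limit, and a count of all values below that limit taken from the measurements themselves.

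A reader might also carry the crude Phase 1 rate (2 of 66 on RPC1063) over to the Part A arms. The documents do not support that: both cases were at 2 mg, above the 0.5 mg and 1 mg of Part A, and the number treated at 2 mg is not given.

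On the ratio, protocol 11.2.1 mentions it once, in text on spirometry technique, and promises calculation rather than tabulation by arm. It is not a named endpoint and can be derived from the listing. The SAP (V1.2, May 2014) also predates protocol Version 4.0 (October 2014). These points lower its weight, but the two documents still need to agree.

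Finally, the protocol asks only for descriptive characterisation of pulmonary toxicity, and the table shells are not available here, so a count may be planned there. SAP 10.5 as written does not call for one. The 20% cut describes the Phase 1 cases and is not a protocol threshold; it is proposed only for reporting. A count at the 70%-of-predicted entry limit is not proposed, because a patient enrolled just above it could cross it through ordinary variation.

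**Conclusion.** The point holds as a gap in descriptive safety reporting. The pulmonary tables in SAP 10.5 give the centre, spread and extremes of FEV1 and FVC, but not the number of patients per arm with a marked decline, while the same SAP gives such counts for three other safety domains. The FEV1/FVC ratio in protocol 11.2.1 has no counterpart in SAP 10.5.

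The gap in counts and the missing ratio follow from the text alone. The numerical illustration rests on an assumed fall of 25% in two of 70 patients, an assumed SD of 5 to 12 and approximate normality. It does not predict how many cases Part A will see. Data collection, error rates and sample size are not affected. Severity is minor to moderate.

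**What to change.** Reporting only; no clinical rule changes.

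1. Add to SAP 10.5, per arm, at each scheduled visit and at any time after baseline, the number and percent of patients with (a) FEV1 or FVC more than 20% below baseline and (b) FEV1 or FVC below 50% of predicted, with patients tested as the denominator.
2. Reconcile SAP 10.5 with protocol 11.2.1: summarise the FEV1/FVC ratio (actual value and change), or state why it is dropped.

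The cost is one derived variable and one or two descriptive tables, all from spirometry already collected.
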